6.1.2.2 DOSING AND ADMINISTRATION OF T-VEC

The total volume of T-VEC to be prepared will be based on investigator evaluation of injectable lesions and estimation of the total volume needed based on the T-VEC injection volume guideline based on tumor size table (see below).

The maximum volume of T-VEC administered at any dose is 4.0 mL for any individual lesion. The maximum dose in any one treatment is 4.0 mL. Use the maximum amount whenever lesions allow.

The recommended volume of T-VEC to be injected into the tumor is dependent on the size of the tumor on ultrasonography on the day of injection and should be determined according to the injection volume guideline in the following table:

T-VEC Injection Volume Guideline Based on Tumor Size

Tumor Size (longest dimension)	Maximum Injection Volume
> 5.0 cm	4.0 mL
> 2.5 cm to 5.0 cm	2.0 mL
> 1.5 cm to 2.5 cm	1.0 mL
> 0.5 cm to 1.5 cm	0.5 mL

≤ 0.5 cm	0.1 mL
---------------	--------

Administration of T-VEC will follow the specific guidelines and procedure outlined in the Pharmacy Information Guide.

6.1.2.3 DOSING DELAYS/DOSE MODIFICATIONS

If talimogene laherparepvec treatment was delayed by > 2 weeks, that dose will be deemed to have been missed and the subject will proceed to the next scheduled treatment visit. Dose reductions of talimogene laherparepvec are not permitted, other than a reduction in the volume injected due to a disease response.

If a subject experiences any of the following treatment-related toxicities, talimogene laherparepvec administration should be delayed until the toxicity has resolved to at least CTCAE grade 1 or baseline:

- grade 2 or greater immune-mediated adverse events, with the exception of vitiligo.
- grade 2 or greater allergic reactions.
- any other grade 3 or greater hematologic or non-hematologic toxicity.

Subjects who are receiving talimogene laherparepvec may not receive systemic antiherpetic drugs (eg, acyclovir, valacyclovir, famciclovir), but may receive a topically administered antiherpetic drug more than 20 cm from a talimogene laherparepvec injection site. Dosing should be permanently discontinued if, in the opinion of the investigator, the subject develops clinical evidence of any systemic herpes infection (such as encephalitis or disseminated infection). If the subject requires corticosteroid dosing of > 10 mg prednisone daily (or equivalent) for related toxicities, talimogene laherparepvec dosing must be withheld until the corticosteroid dose has decreased to < 10 mg prednisone daily (or equivalent).

If talimogene laherparepvec dosing is delayed by more than 4 weeks from the date of the planned dose (ie, approximately 6 weeks or 7 weeks depending whether the patient is receiving Q2W or Q3W dosing from the previous dose) due to the occurrence of an adverse event that is considered related to talimogene laherparepvec, the subject must be permanently withdrawn from talimogene laherparepvec treatment.

Talimogene laherparepvec is to be permanently discontinued for subjects meeting any of the following criteria:

- The subject, for any reason, requires treatment with another anticancer therapeutic agent for treatment of the study disease. In this case, discontinuation from the treatment occurs immediately upon introduction of the new agent.
- Increase in size ≥ 2 -fold within 4 months of first injection. Patients who develop new locoregional disease during treatment may be treated additionally with the study agent at the PI discretion, in keeping with standard practice for other cancer histologies.
- A grade 2 or greater immune-mediated adverse event (with the exception of vitiligo) or allergic reactions attributed to talimogene laherparepvec that would require a dose delay of greater than 4 weeks from the date of the planned dose (ie, approximately 6 weeks from the previous dose). NOTE: immune-mediated glomerulonephritis, vasculitis, and pneumonitis and exacerbation of psoriasis have been observed in subjects receiving talimogene laherparepvec in clinical trials. Most of these subjects had a history of other autoimmune disease and/or prior treatment with agents that offered plausible alternative etiologies, however, immune-mediated adverse events can potentially involve any organ system.
- Any other talimogene laherparepvec-related non-hematologic or hematologic toxicities grade 3 or greater occur that, in the opinion of the investigator, would require a dose delay of greater than 4 weeks from the date of the planned dose (ie, approximately 6 weeks from the previous dose).
- The subject develops clinical evidence of any systemic herpes infection (such as encephalitis or disseminated infection).
- A female subject becomes pregnant or fails to use acceptable method(s) of effective contraception (for those subjects who are able to conceive).
- A female subject breast feeds while on study treatment.

- Concurrent medical illness that, in the judgment of the investigator, would make continued treatment with talimogene laherparepvec dangerous for the subject.

6.1.3 DURATION OF THERAPY

Patients will be treated for a maximum of 52 weeks with intralesional injection occurring every 2 weeks.

6.1.4 DEFINITION OF DOSE-LIMITING TOXICITY

N/A

6.2 PREPARATION/HANDLING/STORAGE/ACCOUNTABILITY

6.2.1 ACQUISITION AND ACCOUNTABILITY

T-VEC is provided by Amgen Inc.

T-VEC is available as open-label bulk supply that can be used across study participants. T-VEC is supplied in two concentrations, and the concentration that is to be prepared will be based on which visit the administration will occur on:

- T-VEC at nominal concentration of 10^6 PFU/mL with approximately 1.15 mL in a 2 cc vial for the initial dose
- T-VEC at nominal concentration of 10^8 PFU/mL with approximately 1.15 mL in a 2 cc vial for the second and all subsequent doses

Transfer of T-VEC in original packaging or after preparation between clinical sites is not permissible. Contact the study sponsor or Amgen to discuss alternatives for a shipment to arrive at the site where the product is needed.

6.2.2 FORMULATION, APPEARANCE, PACKAGING, AND LABELING

T-VEC will be presented as a sterile, semi-translucent to opaque suspension, practically free from particles, preservative-free frozen liquid in a single-use 2.0 cc Crystal Zenith Resin vial. Each vial will contain T-VEC at a nominal concentration of 10^6 PFU/mL or 10^8 PFU/mL for intratumoral injection in a solution containing disodium hydrogen phosphate dihydrate, sodium dihydrogen phosphate dihydrate, sodium chloride, sorbitol, myo-inositol, and water for injection vials are appropriately filled to ensure that a sufficient deliverable dose is provided. Each vial is intended for single use only. Vials will be sealed with gray rubber stoppers, Fluorotec-coated on the product side. The vial caps will be color coded and may be used to help distinguish between the 10^6 PFU/mL and 10^8 PFU/mL vial concentrations.

Information provided on the labels for T-VEC will comply with ICH, GCP, and local regulatory requirements.

6.2.3 PRODUCT STORAGE AND STABILITY

Refer to Pharmacy Information Guide

6.2.4 PREPARATION

Refer to Pharmacy Information Guide

6.3 MEASURES TO MINIMIZE BIAS: RANDOMIZATION AND BLINDING

This is a single arm, open label study and therefore no blinding or randomization will be used. Bias will be minimized by the photographic documentation of any measurements that document clinical response.

6.4 STUDY INTERVENTION COMPLIANCE

Injection will be performed only by active staff physicians with privileges for “Intralesional Chemotherapy Injections.” Any measurements which result in clinical response will be documented by photograph.

6.5 CONCOMITANT THERAPY

N/A

6.5.1.1 EXCLUDED TREATMENTS, MEDICAL DEVICES, AND/OR PROCEDURES DURING STUDY PERIOD

Subjects must not use any of the following therapies during screening or treatment period, unless indicated otherwise:

- Other investigational agents
- Concurrent experimental or approved antitumor therapies other than the study drugs
- Systemic immunosuppressive agents used on an ongoing basis during administration of T-VEC
- Any live vaccine therapies used for the prevention of infectious disease within 28 days prior to enrollment and during treatment period. Examples of live vaccines include, but are not limited to, the following: measles, mumps, rubella, chicken pox, yellow fever, rabies, BCG, and typhoid (oral) vaccine. Seasonal influenza vaccines for injection are generally killed virus vaccines and are allowed. However, intranasal influenza vaccines (eg, Flu - Mist®) are live attenuated vaccines and are not allowed
- Participants may not receive systemic antiherpetic drugs (eg, acyclovir, valacyclovir, famciclovir) but may receive a topically administered antiherpetic drug more than 20 cm from a T-VEC injection site

6.5.2 RESCUE MEDICINE

Grade 1 to 2 allergic reactions or febrile states caused by T-VEC cytokine release can be treated with antihistamines and/or acetaminophen as required. In the event any cellulitis is suspected, then appropriate antibiotic therapy should be instituted immediately and further injections stopped until the infection has resolved.

7 STUDY INTERVENTION DISCONTINUATION AND PARTICIPANT DISCONTINUATION/WITHDRAWAL

7.1 DISCONTINUATION OF STUDY INTERVENTION

Discontinuation from T-VEC does not mean discontinuation from the study, and remaining study procedures should be completed as indicated by the study protocol. If a clinically significant finding is identified (including, but not limited to changes from baseline) after enrollment, the investigator or qualified designee will determine if any change in participant management is needed. Any new clinically relevant finding within 4 weeks of last T-VEC injection will be reported as an adverse event (AE).

In the absence of treatment delays due to adverse events, treatment may continue for 12 months or until one of the following criteria apply:

1. Complete response with no cutaneous angiosarcoma to inject
2. Disease progression as per section 8.1.2.3
3. Deterioration in performance status precluding further treatment
4. G4/5 adverse events persisting ≥ 2 weeks
5. Patient decides to withdraw from the study, or
6. PI decision

7.2 PARTICIPANT DISCONTINUATION/WITHDRAWAL FROM THE STUDY

Participants are free to withdraw from participation in the study at any time upon request.

An investigator may discontinue or withdraw a participant from the study for the following reasons:

- Pregnancy
- Significant study intervention non-compliance
- If any clinical adverse event (AE), laboratory abnormality, or other medical condition or situation occurs such that continued participation in the study would not be in the best interest of the participant
- Disease progression which requires discontinuation of the study intervention
- If the participant meets an exclusion criterion (either newly developed or not previously recognized) that precludes further study participation
- Participant unable to receive T-VEC injection for ≥ 4 weeks (two consecutive doses).

The reason for participant discontinuation or withdrawal from the study will be recorded within the patient's medical record and OnCore and/or the Clinical Trial Management System (CTMS). Subjects who sign the informed consent form but do not receive the study intervention may be replaced. Subjects who sign the informed consent form, receive the study intervention, and subsequently withdraw, or are withdrawn or discontinued from the study prior to becoming evaluable for objective response, may be replaced.

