8.1.2 EFFICACY ANALYSES

For the purposes of meeting the secondary endpoints of this study, patients will be re-evaluated for response every 2 weeks prior to injection using physical examination and measurement with calipers and/or ruler.

In addition to baseline imaging, imaging should also be obtained 12 weeks following initial documentation of objective response.

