8.1.2.1 DEFINITIONS

Evaluable for toxicity. All patients will be evaluable for toxicity from the time of their first treatment with T-VEC

Evaluable for objective response. Only those patients who have measurable disease present at baseline, have received at least three injections at the 10^8 dose level, and have had their disease re-evaluated will be considered evaluable for response. These patients will have their response classified according to the definitions stated below.

Evaluable Non-Target Disease Response. Patients who have lesions present at baseline that are evaluable but do not meet the definitions of measurable disease, have received at least one cycle of therapy, and have had their disease re-evaluated will be considered evaluable for non-target disease. The response assessment is based on the presence, absence, or unequivocal progression of the lesions.

Disease Parameters

Measurable disease. Measurable lesions are defined as those that can be accurately measured in at least one dimension (longest diameter to be recorded) as ≥ 6 mm by calipers on clinical examination. All tumor measurements must be recorded in millimeters (or decimal fractions of centimeters).

Non-measurable disease. All other lesions (or sites of disease), including small lesions (longest diameter < 6 mm) are considered non-measurable disease.

Note: Cystic lesions that meet the criteria for radiographically defined simple cysts should not be considered as malignant lesions (neither measurable nor non-measurable) since they are, by definition, simple cysts.

“Cystic lesions” thought to represent cystic metastases can be considered as measurable lesions if they meet the definition of measurability described above. However, if non-cystic lesions are present in the same patient, these are preferred for selection as target lesions.

Target lesions. All measurable lesions up to a maximum of 5 lesions in total, representative of all involved organs, should be identified as **target lesions** and recorded and measured at baseline. Target lesions should be selected on the basis of their size (lesions with the longest diameter), but in addition should be those that lend themselves to

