9.3 POPULATIONS FOR ANALYSES

The analysis datasets (e.g., which participants will be included in each analysis) include the following:

- Intention-to-Treat (ITT) Analysis Dataset
- Safety Analysis Dataset: defines the subset of participants for whom safety analyses will be conducted (e.g., participants who took at least one dose of study intervention)
- Per-Protocol Analysis Dataset: defines a subset of the participants in the full analysis (ITT) set who complied with the protocol sufficiently to ensure that these data would be likely to represent the effects of study intervention according to the underlying scientific model (e.g., participants who took at least 80% of study intervention for 80% of the days within the maintenance period)

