9.4.2 ANALYSIS OF THE PRIMARY EFFICACY ENDPOINT(S)

Our primary endpoint for this analysis will be confirmed overall response rate (ORR) in injected lesions based on modified RECIST criteria appropriate for cutaneous neoplasms (ORR = complete response + partial response)

According to the Simon's two-stage design, after testing the treatment on 8 patients in the first stage, the trial will be terminated if 1 or fewer responds. If the trial goes on to the second stage, a total of 13 patients will be studied. If the total number responding is less than or equal to 3, the treatment is rejected. Please see Sample Size description above for further details.

In addition, we will construct a 95% exact confidence interval for the ORR.

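### Section 7.2 lets treated patients who leave before evaluability, including for progression or toxicity, be replaced, and no text counts them as non-responders, so the ORR can be biased upward

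*Combined protocol and SAP*

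**What the plan says.** **Replacement.** Section 7.2 allows replacement of patients who consent, receive T-VEC and "subsequently withdraw, or are withdrawn or discontinued from the study prior to becoming evaluable for objective response, may be replaced". The sentence is permissive and sets no limit by reason. Among the reasons for which the investigator may withdraw a patient from the study, the same section lists "Disease progression which requires discontinuation of the study intervention", as well as adverse events. It also provides that "The reason for participant discontinuation or withdrawal from the study will be recorded".

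**Evaluability.** Section 8.1.2.1 admits to the response assessment only patients who have measurable disease at baseline, "have received at least three injections at the 10^8 dose level, and have had their disease re-evaluated will be considered evaluable for response". It continues: "These patients will have their response classified according to the definitions stated below".

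**Stopping drug versus leaving the study.** Section 7.1 treats these as different events. Ending T-VEC does not by itself take a patient off study, and so does not by itself trigger replacement.

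**Analysis.** Section 9.3 lists an "Intention-to-Treat (ITT) Analysis Dataset" and, when defining the per-protocol set, refers to ITT as the full analysis set. It does not say which patients ITT contains or that the ORR uses it. Section 9.4.2 begins "Our primary endpoint for this analysis will be confirmed overall response rate (ORR) in injected lesions" and gives the two-stage rule and an exact interval. It names no analysis set and has no rule for patients who never become evaluable. The response table in 8.1.2.3 has no not-evaluable category.

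**The concern.** The trial stops if 1 or fewer of the first 8 patients respond and succeeds if 4 or more of 13 respond. With counts this small, who enters the 8 and the 13 matters.

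A patient who progresses or has serious toxicity in the first two months is a treatment failure. If that patient leaves the study, 7.2 allows a substitute. If the patient only stops T-VEC before the third 10^8 dose, replacement is not triggered, but evaluability can never be reached, and no text says how the patient counts. A patient who fails after evaluability stays in the denominator. Failures are thus handled differently according to when they occur, and the choice to withdraw and replace belongs to an investigator who knows how the patient is doing.

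The failures can be seen in this window: 8.1.2 says "patients will be re-evaluated for response every 2 weeks prior to injection", and 8.1.2.3 defines progression as a 20% increase or any new lesion. At stake are the ORR and the two-stage decision, not the other endpoints.

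**Working it through.** **1. Length of the window.** From 6.1.2.1: dose 1 (10^6) on day 0, dose 2 three weeks later, then every two weeks. The 10^8 doses fall on days 21, 35 and 49, that is, weeks 4, 6 and 8. The next visit is day 63 (week 10). Evaluability is reached at about week 8, or week 10 if the re-evaluation must follow the third 10^8 dose.

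**2. The plan's own figures (9.2).** For a response rate p among the patients counted,

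P(success) = Σ over x = 2 to 8 of b(8, x, p) × P(X₂ ≥ 4 − x), with X₂ ~ Bin(5, p).

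At p = 0.10: 0.1488 × 0.0815 + 0.0331 × 0.4095 + 0.0050 = 0.0307 (stated 0.031). P(X ≤ 1 of 8) = 0.813 (stated 0.813). At p = 0.40, power is 0.8015, so type II error is 0.198 (stated 0.198). The design arithmetic is right.

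**3. Effect of replacement.** Let m patients be replaced for every 13 counted, so the replaced share of treated patients is f = m/(13 + m). Let k be the response rate that replaced patients would have had, divided by the rate among evaluable patients. If 10% is the rate among all treated patients, the rate among those counted is

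p = 0.10 / (1 − f(1 − k)).

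The same rule is then evaluated at this p, with the same share assumed in both stages. The values of m and k are assumptions; the documents give neither.

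| m per 13 | f | p (k = 0) | Type I error (k = 0) | p (k = 0.5) | Type I error (k = 0.5) |
|---|---|---|---|---|---|
| 0 | 0 | 0.1000 | 0.031 | 0.1000 | 0.031 |
| 1 | 0.071 | 0.1077 | 0.039 | 0.1037 | 0.035 |
| 2 | 0.133 | 0.1154 | 0.049 | 0.1071 | 0.038 |
| 3 | 0.188 | 0.1231 | 0.059 | 0.1103 | 0.042 |

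Example for m = 3, k = 0: 0.1929 × 0.1175 + 0.0541 × 0.4814 + 0.0106 = 0.059.

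k = 0 is the worst case. k = 0.5 allows for late responders; 2.3.2 reports a median time to response of 16 weeks (range 8 to 32) with a T-VEC combination. The 0.050 target is reached at p = 0.1165. That is f = 0.141 (about 2.1 replacements per 13) for k = 0, and f = 0.283 (about 5.1 per 13) for k = 0.5.

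**4. The other reading.** If 10% and 40% were meant among evaluable patients, p stays 0.10 under the null and type I error stays 0.031.

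**5. Effect on the estimate.** Four responders among 13 counted is 30.8% (exact 95% CI 9.1% to 61.4%). With three replaced non-responders put back, it is 4/16 = 25.0% (7.3% to 52.4%).

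**The case against.** The strongest reply is that this is a response-evaluable design fixed in advance: 8.1.2.1 sets a minimum exposure, 7.2 ties replacement to it, and the minimum has a reason, since the first dose is low to allow seroconversion. On that reading type I error is as stated. This stands as a possible reading, and the plan does not say where its 10% comes from. But no section says that the rates describe evaluable patients. Section 9.2 speaks of patients, and the endpoint definition of a proportion of patients. Even on this reading, the reported ORR would describe only patients who lasted about two months, and the plan should say so.

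Several stronger readings are tempting and should be resisted:

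- *Type I error exceeds 0.050.* The documents do not show this. It needs an all-treated 10% and, even in the worst case, three replacements per 13.
- *Every early progressor will be dropped.* Replacement is optional and requires leaving the study. Section 6.1.2.3 also lets the investigator keep treating patients with new locoregional disease.
- *There is no full analysis set.* ITT is named as one. It is simply not assigned to the ORR.
- *No treated patient should ever be replaced.* That would also make non-responders of patients lost to pregnancy, withdrawn consent or late-found ineligibility. It is a trade-off, not a correction.

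**Conclusion.** The concern holds as a gap in the rules, not as an arithmetic error. Followed as written, the plan allows early treatment failures to be left out of the stage 1 and final counts at an unblinded investigator's discretion, and this can bias the ORR upward.

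The size is modest with few replacements. Under an all-treated null of 10%, one to three replacements per 13 move type I error from 0.031 to between 0.039 and 0.059 in the worst case, or to between 0.035 and 0.042 if replaced patients would respond at half the evaluable rate. If 10% was meant among evaluable patients, there is no inflation, only a narrower population than the label ORR suggests. Confidence is medium, because the number of replacements and the population behind the 10% are not stated. The point deserves a change because the counts are small and the remedy is only wording.

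**What to change.** 1. In 7.2, add: *A treated patient who leaves before becoming evaluable because of disease progression, death, or toxicity related to T-VEC, or who starts new anticancer therapy, is not replaced and counts as a non-responder at stage 1 and in the final analysis.* Replacement for reasons unrelated to efficacy or drug toxicity may stay. The withdrawal reasons already recorded make the rule workable.
2. In 9.4.2, state this denominator for both stages. Say explicitly that a patient who stops T-VEC for one of these reasons before the third 10^8 dose, but stays on study, is also in it as a non-responder. Report in addition the ORR with its exact 95% CI among all patients who received T-VEC.

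**Cost.** No visits are added. The ORR may be slightly lower. If 40% describes all treated patients, counting failures this way leaves the design power at 0.80. If 40% was meant only among evaluable patients, power falls: with 10% of treated patients counted as early failures, p = 0.40 × 0.90 = 0.36 and power is 0.713 instead of 0.802. Larger shares cost more (0.605 at 20%, 0.483 at 30%). The sponsor should therefore settle which population the two rates describe before stage 1 is read. Label: cheap improvement.
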